**Source of Subjects Enrolled in the Ivacaftor Arm**

- Subjects who completed ivacaftor treatment in Study 124 Part B
- Subjects who did not participate in Study 124 Part B (e.g., subjects who participated in Study 124 Part A only and subjects who did not participate in Study 124 Part A or B) and are <24 months of age at Day 1 of Study VX15-770-126 (Study 126)

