## 8.3 Observational Arm

### 8.3.1 Inclusion Criterion

1. Completed ivacaftor treatment in Study 124 Part B and elected not to enroll in the ivacaftor arm of Study 126, or received at least 1 dose of ivacaftor and prematurely discontinued ivacaftor treatment in Study 124 Part B and received at least 1 dose of ivacaftor treatment in Study 124 Part B

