### **12.3 Statistical Analysis**

Data from all endpoints will be summarized using descriptive statistics and presented by subjects from Study 124 Part B/subjects not from Study 124 Part B, and by study visit. No inferential analyses are planned.

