During the course of study conduct, if ivacaftor is approved and available for the treatment of CF in populations enrolled in this study, and if a subject chooses to move onto commercially available ivacaftor, the ETT Visit (Section 9.1.1.5) will be completed before dosing with commercial drug begins, and the Safety Follow-up Visit and Follow-up OE will not be required.

Table 3-1 Footnote “a”

The ETT Visit is to be scheduled as soon as possible after the last dose of ivacaftor. If the ETT Visit occurs 3 weeks or later after the last dose of ivacaftor, the Safety Follow up Visit will not be required. Subjects who elect to receive commercially available ivacaftor will be discontinued from ivacaftor dosing and will complete the ETT Visit ~~and Follow-up OE.~~

Table 3-1 Footnote “b”

For subjects who elect to receive commercially available ivacaftor, the Safety Follow-up Visit *and Follow-up OE* will not be required.

Additional Clarifications

The following are provided to correct minor inconsistencies:

Table 3-1 Footnote “d”

Study Drug Dose Determination is not to be performed at the Week 96 Visit because it is the final visit of the treatment period.

Tertiary Endpoint “weight-for-length-for-age z-score”

The term “weight-for-length-for-age z-score” is not the appropriate name for this endpoint. The correct name is “weight-for-length z-score” in the following sections of the protocol: Sections 2 Synopsis (Assessments); 7.1.3 Tertiary Endpoints; 9.2.3 Rationale for Study Assessments (Measures of Nutritional Status); 11.5.1 Measures of Nutritional Status; and 12.3.3.3 Analysis of Tertiary Variables.

In addition, the final analysis will be based on the combined subjects from Study 124 Parts B and A/B, and subjects not from Study 124 Parts B and A/B.

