6.2 Sample Size and Power

The study is not powered to detect a significant treatment effect. The study will enroll approximately 75 subjects.

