7.2 Observational Arm Analysis Set

As no subjects enrolled in the Observational Arm, the Observational Arm Analysis Set will not be defined. Statistical Analysis

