For the Ivacaftor Arm, the TE period will include the time period starting from the first dose date of the study drug in the current study to the Safety Follow-up Visit, or the last dose date + 28 days for subjects who do not have a Safety Follow-up Visit. The TE period will be used for safety analyses unless specified otherwise.

Unscheduled visits: Unscheduled visit measurements will be included in analysis as follows:

- In scheduled visit windows per specified visit windowing rules
- In the derivation of baseline/last on-treatment measurements.
- In the derivation of maximum/minimum on-treatment values and maximum/minimum change from baseline values for safety analyses.
- In individual subject data listings as appropriate.

Visit windowing rules: The analysis visit windows for protocol-defined visits in the Ivacaftor Arm are provided in Appendix B. The windows will be applied using the following rules for both scheduled and unscheduled visits. If no measurement is available within a visit window, the assessment will be considered missing for the visit. If there is more than one measurement available within the same visit window, the following rules will be used:

- For all safety parameters, if there are multiple measurements within a visit window, then 1) the record closest to the target day will be used, with the exception of the threshold analysis in which the worst record will be used; 2) if there are multiple records within the same distance of the target day, the latest record will be used; or 3) the Safety Follow-Up (SFU) visit will not be windowed; instead, the nominal visit will be used in relevant analyses.
- For all efficacy parameters, if there are multiple measurements within a visit window, the record at the scheduled visit will be used. Otherwise,
 - If there are no measurements at the scheduled visit, then the record closest to the target day will be used;

- If there are multiple records with the same distance to the target day, the latest record will be used.
- Assessments at the early treatment termination (ETT) visit will follow the windowing rules for regular visits, with the exception of the ETT visit occurs 21 days or later after the last dose, which will be treated as SFU visit.

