8.4 Safety Analysis

The overall safety profile of study drug will be assessed in terms of the following safety and tolerability endpoints:

- Treatment-emergent adverse events (TEAEs)
- Clinical laboratory values (hematology and serum chemistry)
- Standard 12-lead electrocardiograms
- PEs (clinically significant abnormalities recorded as medical history or adverse events)
- Vital signs (systolic blood pressure, diastolic blood pressure, temperature, pulse rates, and respiratory rate)
- Ophthalmologic examinations

Unless specified otherwise, safety endpoints will be analyzed based on the Safety Set, for the total subjects in the Ivacaftor arm. Only a descriptive analysis of safety will be performed. All safety data will be presented in individual subject data listings. No statistical hypothesis testing will be conducted.

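### Safety tables for the total ivacaftor arm mix children observed from treatment week 1 with Study 124 rollovers observed from about week 25, so harm concentrated early in treatment would be understated

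*SAP*

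**What the plan says.** **Pooling.** SAP section 2.1 states that "the final analysis will be based on the combined subjects from Study 124 Parts B and A/B, and subjects not from Study 124" (meaning those same parts). Read alone, that sentence could mean only that Parts B and A/B are merged with each other. SAP section 8.1 settles it by making the arm overall the default for every analysis, and SAP section 8.4 says "safety endpoints will be analyzed based on the Safety Set, for the total subjects in the Ivacaftor arm". No safety table is specified by source group.

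**Start of counting.** Under SAP section 8.1, "the TE period will include the time period starting from the first dose date of the study drug in the current study". SAP section 8.4.1 classes earlier adverse events as pretreatment and builds the summary tables from TEAEs only; everything else is listed.

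**Who is in the arm.** The protocol synopsis takes "Subjects who completed ivacaftor treatment in Study 124 Part B" and, in addition, children under 24 months who were not in Part B. Protocol section 8.1.1 (criterion 1) requires rollovers to have completed the last Part B visit. Section 8.1.2 gives severe reactions in Study 124 as an example of possible ineligibility.

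**What the protocol planned.** Protocol section 12.3 has data from all endpoints "presented by subjects from Study 124 Part B/subjects not from Study 124 Part B, and by study visit". Protocol section 12.3.4 adds that TEAEs will be assessed overall.

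**Size.** SAP section 6.2: "The study will enroll approximately 75 subjects". No split by source is given.

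**The concern.** The primary objective is safety in children under 24 months at treatment initiation. For rollovers, initiation took place in Study 124. Their first 24 weeks or so on drug lie outside the treatment-emergent period, yet they stay in the Safety Set denominator. Because safety is purely descriptive, the tabulated percentages are the result.

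The point concerns event incidence: TEAEs, serious TEAEs, TEAEs leading to discontinuation, LFT and QTcF threshold counts, and lens opacities. It does not concern change-from-baseline summaries. For a harm that appears mainly in the first months, the pooled percentage is neither the risk for a child starting ivacaftor nor the later risk for a child already established on it. It depends on how many rollovers happened to enrol.

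**Working it through.** **The plan's own figure.** The sample size of about 75 has no formula, effect size or power behind it, so there is nothing to reproduce. The study is declared unpowered, and that is not an error.

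**Time on drug covered by the tables.** Children not from Part B or A/B: treatment weeks 1 to 96. Same-day rollovers: 24 weeks in Study 124 come first, so the tables cover about week 25 to week 24 + 96 = 120.

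**Dilution.** Let w be the rollover share of the Safety Set, p the incidence in new starters and q the incidence in rollovers counted from Study 126 Day 1. Then

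pooled = (1 − w)p + wq, and p − pooled = w(p − q).

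The pooled figure is too low as an estimate of p whenever w > 0 and q < p. It is too high if q > p. The documents give none of w, p or q, so every value below is an assumption.

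*Extreme case, all harm in the first 24 weeks (q = 0), p = 10%:*
- w = 25%: 0.75 × 10% = 7.5%
- w = 50%: 0.50 × 10% = 5.0%
- w = 75%: 0.25 × 10% = 2.5%

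*Graded case, p = 20%.* The cumulative hazard over 96 weeks is H = −ln(0.8) = 0.2231. Let a share s of H fall in weeks 0–24. The rest runs at a constant rate over weeks 24–96 (72 weeks) and continues at that rate to week 120. Rollovers are exposed to it for 96 weeks, so

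q = 1 − exp[−H(1 − s) × 96/72].

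For s = 0.75: H(1 − s) × 96/72 = 0.0558 × 1.333 = 0.0744, so q = 7.2%.

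| s | q | w = 20% | w = 50% | w = 80% |
|---|---|---|---|---|
| 0.25 (constant hazard) | 20.0% | 20.0% | 20.0% | 20.0% |
| 0.50 | 13.8% | 18.8% | 16.9% | 15.1% |
| 0.75 | 7.2% | 17.4% | 13.6% | 9.7% |
| 1.00 | 0% | 16.0% | 10.0% | 4.0% |

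The first row is the null case. If the hazard is constant and completion selects nobody out, the later start costs nothing.

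**Precision.** For early harm the informative denominator is the new starters, not the total. With zero events, the exact two-sided 95% upper limit is 1 − 0.025^(1/n): 4.8% for n = 75, but 13.7% if only 25 are new starters. The chance of seeing at least one event of 5% true incidence is 1 − 0.95^n: 97.9% for 75 against 72.3% for 25.

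**Where the tables are already protected.** In SAP Appendix B only the children not from Part B or A/B have windows at Weeks 2, 4, 8 and 18 (as applicable to each assessment). Early by-visit laboratory and vital-sign summaries are therefore not diluted. TEAE incidence and the LFT and QTcF threshold counts run over the whole treatment-emergent period and have no such protection.

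**The case against.** **Selection is possible, not shown.** A reader might infer that early stoppers were removed, because a child who "received at least 1 dose of ivacaftor and prematurely discontinued ivacaftor treatment in Study 124 Part B" was eligible only for the observational arm and the SAP reports "As no subjects enrolled in the Observational Arm, the Observational Arm Analysis Set will not be defined". The documents do not support that step. The observational arm was also open to completers who declined the ivacaftor arm. An empty arm fits equally well with no Part B child having stopped early, or with those who stopped declining to enrol. No Study 124 discontinuation count is given. Completion is also not the same as tolerance: protocol section 8.1.1 admits, with medical monitor approval, children interrupted at the last visit or not yet through four weeks of rechallenge, and Gap Transition children restart after a break. Their q need not be near zero. All of this stands.

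**No general bias toward apparent safety.** A reader might also infer that every safety percentage is pulled down. That holds only for front-loaded harm. Harm that grows with cumulative exposure could be raised by pooling, because rollovers are observed later in treatment. The documents do not establish that any listed outcome is front-loaded in humans; protocol section 9.2.3 calls the human relevance of the rat lens finding unknown.

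**The protocol is mixed on TEAEs.** Section 12.3 covers all endpoints by source group, but section 12.3.4 has TEAEs assessed overall. Section 12.3.4.1 says only by treatment, a term tied to the two sources only in the efficacy sections. An overall TEAE column therefore has protocol support and should stay.

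**Nothing is concealed.** The pooling is declared in SAP section 2.1, all safety data are listed by subject, and rollovers' early events belong to Study 124. True, but listings and another study's report do not supply an early incidence in any Study 126 summary table.

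**Conclusion.** The concern holds in conditional form. The SAP drops the source-group presentation without giving a reason and specifies neither exposure-adjusted event rates nor a summary by time since first ivacaftor dose. For harm concentrated in the first months, the total-arm incidence falls below the new-starter incidence by w(p − q).

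The size cannot be fixed from the documents. It ranges from nothing (constant hazard, no selection) to a relative loss equal to the rollover share itself when all harm falls in the first 24 weeks: 20% to 80% for assumed shares of 20% to 80%. Selection of rollovers for tolerability is allowed by the eligibility rules but not demonstrated. This is a gap in presentation on the primary endpoint, not an error of calculation.

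**What to change.** Keep the total column. Beside it add two columns, 'Study 124 Part B or A/B rollover' and 'not from Study 124 Part B or A/B', in the tables of TEAEs, serious TEAEs, TEAEs leading to discontinuation, LFT and QTcF thresholds, lens opacities and exposure.

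- Footnote the total as excluding rollovers' Study 124 events.
- Footnote the second group as possibly including Part A-only children with prior dosing. SAP section 8.1 calls everyone outside Parts B and A/B ivacaftor-naïve, but the protocol synopsis admits Part A-only subjects, and protocol section 9.4 refers to safety and PK data from Part A. The length of Part A dosing is not stated in these documents.
- Show rollover exposure twice: within Study 126, and cumulatively from the first Study 124 dose.

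The cost is SAP wording and two columns per table. Appendix B already separates the groups, and no new data are collected in Study 126; cumulative exposure needs only the rollovers' Study 124 dosing dates. The drawback is smaller denominators, with correspondingly wider intervals in each column.

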2.2 Modifications to the Approved Statistical Analysis Plan

Not applicable.

3 INTRODUCTION

This statistical analysis plan (SAP) Methods is for the final analysis for the VX15-770-126 study and is based on the approved clinical study protocol (CSP), dated 05 October 2017, version 2.0.

Study VX15-770-126 is a phase 3, 2-arm, open-label study to evaluate the safety and pharmacodynamics of long-term ivacaftor treatment in subjects with cystic fibrosis who are less than 24 months of age at treatment initiation and have an approved ivacaftor-responsive mutation.

This SAP (Methods) documents the planned final statistical analysis of efficacy and safety endpoints defined in the study protocol of VX15-770-126.

The Vertex Biometrics Department will perform the final statistical analysis of the efficacy and safety data; SAS® Version 9.4 Software (SAS Institute, Cary, North Carolina, USA) or higher will be used to generate all statistical outputs (tables, figures, listings and datasets).

The SAP (Methods) for the final analysis will be finalized and approved before the database lock for the final analysis. Any changes made to the SAP Methods after the database lock has occurred will be documented in the clinical study report for the final analysis.

4 OBJECTIVES

4.1 Primary Objective

Ivacaftor Arm:

To evaluate the safety of long-term ivacaftor treatment in subjects with CF who are <24 months of age at treatment initiation and have an approved ivacaftor-responsive mutation.

Observational Arm:

To evaluate the long-term safety after discontinuation of ivacaftor treatment in subjects with CF who were <24 months of age at treatment initiation and have an approved ivacaftor-responsive mutation.

4.2 Secondary Objectives

Ivacaftor Arm:

To evaluate the pharmacodynamics (PD) of long-term ivacaftor treatment in subjects with CF who are <24 months of age at treatment initiation and have an approved ivacaftor-responsive mutation.

Observational Arm:

Not applicable.

4.3 Tertiary Objectives

Ivacaftor Arm:

To evaluate the efficacy of long-term ivacaftor treatment in subjects with CF who are <24 months of age at treatment initiation and have an approved ivacaftor-responsive mutation.

Observational Arm:

Not applicable.

5 STUDY ENDPOINTS

5.1 Efficacy Endpoint

5.1.1 Primary Efficacy Endpoint

Not applicable.

5.1.2 Secondary Efficacy/Pharmacodynamic Endpoints

Ivacaftor Arm:

Absolute change from baseline in sweat chloride through Week 96

Observational Arm:

Not applicable.

5.1.3 Tertiary Endpoints

Ivacaftor Arm:

- Absolute change from baseline through Week 96 for the following endpoints:
 - Weight
 - Length (assessed as height, as age appropriate)
 - Weight-for-length
 - Weight-for-age z-score
 - Length-for-age z-score
 - Weight-for-length z-score
 - BMI
 - BMI-for-age z-score
 - Lung clearance index (LCI) at qualified study sites
 - Fecal elastase-1
 - Markers of intestinal inflammation
 - Qualitative microbiology cultures
- Annualized rate of pulmonary exacerbations
- Rate of CF-related hospitalizations

Observational Arm:

Not applicable

5.2 Safety Endpoints

Ivacaftor Arm:

Safety, as determined by adverse events (AEs), laboratory values (serum chemistry and hematology), 12-lead ECGs and vital signs, and ophthalmologic examinations (OEs)

Observational Arm:

[figure not shown]
Safety after stopping ivacaftor treatment in Study VX15-770-124 (Study 124) Part B as determined by serious adverse events (SAEs) and results from an OE approximately 24 weeks after the last dose of ivacaftor in Study 124 Part B

6 STUDY DESIGN

6.1 Overall Design

This is a Phase 3, 2-arm, multicenter study with an open-label ivacaftor arm and an observational arm. The study design is shown in [Figure 6-1](#).

Figure 6-1: VX15-770-126 Study Design

- ^a For subjects who have a Same-day Transition, the Week 24 Visit of Study 124 Part B or Part A/B will be the same day as the Day 1 Visit of Study 126. For subjects who have a Gap Transition, the last study visit of Study 124 Part B or Part A/B will not be the same day as the Day 1 Visit of Study 126.
- ^b Day 1 for subjects in the observational arm can be the last study visit of Study 124 Part B.
- ^c The Follow-up OE in the observational arm can be performed in Study 124.
- ^d Only for subjects who received at least 4 weeks of study drug in Study 124 Part B.

6.2 Sample Size and Power

The study is not powered to detect a significant treatment effect. The study will enroll approximately 75 subjects.

6.3 Randomization

Not applicable; treatment dose assignments in this study are determined by age and weight.

6.4 Blinding and Unblinding

Not applicable; this is an open-label study.

7 ANALYSIS SETS

7.1 Ivacaftor Arm Analysis Set

7.1.1 All Subjects Set

The All Subjects Set will be defined as all subjects who are enrolled in the current study. This analysis set will be used for all individual subject data listings and the disposition summary table, unless specified otherwise.

7.1.2 Full Analysis Set

The Full Analysis Set (FAS) will be defined as all subjects who are enrolled and receive at least 1 postbaseline efficacy assessment in the current study. The FAS will be used for all efficacy analyses, unless specified otherwise.

7.1.3 Safety Set

The Safety Set will be defined as all subjects who receive at least 1 dose of study drug in the current study. The Safety Set will be used for all safety analyses, unless specified otherwise.

7.2 Observational Arm Analysis Set

As no subjects enrolled in the Observational Arm, the Observational Arm Analysis Set will not be defined. Statistical Analysis

8 STATISTICAL ANALYSIS

8.1 General Considerations

The Schedule of Assessments is provided in [Appendix A](#). The precision standards for reporting safety and efficacy variables are provided in an internal Biometrics document that specifies the programming rules including the precision for derived variables.

All individual subject data for subjects who are enrolled in the current study will be presented in individual subject data listings.

As no subjects are enrolled in the Observation Arm, all analyses will be done for subjects from the Ivacaftor Arm only. All analysis will be performed for the Ivacaftor Arm overall, unless otherwise specified.

Continuous variables will be summarized using the following descriptive summary statistics: the number of subjects (n), mean, standard deviation (SD), standard error (SE), median, minimum value (min), and maximum value (max). 95% confidence intervals (CI) may be provided as appropriate.

Categorical variables will be summarized using counts and percentages. 95% CI may be provided as appropriate.

Baseline value is defined in two different ways:

Study 124 baseline: the baseline value for rollover subjects (who participated in Study 124 Part B or Part A/B) is defined as the baseline measurement from Study 124 Part B or Part A/B. That is, the most recent non-missing measurement collected on or before the initial

administration of study drug in Study 124 Part B or Part A/B. Note that this definition is consistent with the definition of baseline in Study 124 and applies to both scheduled and unscheduled measurements; if an unscheduled value is the most recent non-missing measurement, it will be used as baseline.

Study 126 baseline: the baseline value for IVA-naïve subjects (who did not participate in Study 124 Part B or Part A/B) is defined as the most recent non-missing measurement collected on or before the initial administration of study drug in the current study, including both the scheduled and unscheduled measurements.

Change (absolute change) from baseline will be calculated as Postbaseline value – Baseline value.

Relative change from baseline will be calculated and expressed in percentage as 100% × (Postbaseline value – Baseline value)/Baseline value.

Treatment-emergent (TE) Period

For the Ivacaftor Arm, the TE period will include the time period starting from the first dose date of the study drug in the current study to the Safety Follow-up Visit, or the last dose date + 28 days for subjects who do not have a Safety Follow-up Visit. The TE period will be used for safety analyses unless specified otherwise.

Unscheduled visits: Unscheduled visit measurements will be included in analysis as follows:

- In scheduled visit windows per specified visit windowing rules
- In the derivation of baseline/last on-treatment measurements.
- In the derivation of maximum/minimum on-treatment values and maximum/minimum change from baseline values for safety analyses.
- In individual subject data listings as appropriate.

Visit windowing rules: The analysis visit windows for protocol-defined visits in the Ivacaftor Arm are provided in Appendix B. The windows will be applied using the following rules for both scheduled and unscheduled visits. If no measurement is available within a visit window, the assessment will be considered missing for the visit. If there is more than one measurement available within the same visit window, the following rules will be used:

- For all safety parameters, if there are multiple measurements within a visit window, then 1) the record closest to the target day will be used, with the exception of the threshold analysis in which the worst record will be used; 2) if there are multiple records within the same distance of the target day, the latest record will be used; or 3) the Safety Follow-Up (SFU) visit will not be windowed; instead, the nominal visit will be used in relevant analyses.
- For all efficacy parameters, if there are multiple measurements within a visit window, the record at the scheduled visit will be used. Otherwise,
 - If there are no measurements at the scheduled visit, then the record closest to the target day will be used;

- If there are multiple records with the same distance to the target day, the latest record will be used.
- Assessments at the early treatment termination (ETT) visit will follow the windowing rules for regular visits, with the exception of the ETT visit occurs 21 days or later after the last dose, which will be treated as SFU visit.
- Assessments at the SFU visit will follow the windowing rules for regular visits if they fall within the upper boundary of the window for the last scheduled visit; it will remain as the SFU if it goes beyond the upper boundary of the window for the last scheduled visit.

Visit windowing rules will not be used for the Observational Arm as they will not add value.

Incomplete/missing data will not be imputed, unless specified otherwise.

Outliers: No formal statistical analyses will be performed to detect or remedy the presence of statistical outliers, unless specified otherwise.

Multiplicity: No multiplicity adjustment will be performed for hypothesis testing.

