8.3 Efficacy Analysis

Statistical methodology will be restricted to descriptive statistics only. Unless specified otherwise, all efficacy analyses described in this section will be based on the FAS, for the Ivacaftor Arm overall.

The analysis will include all available measurements per the visit windowing rules described in [Appendix B](#).

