8.3.3.2 Tertiary Analysis

- The following growth parameters will be summarized descriptively as continuous variables by visit (including change from baseline).
 - Weight
 - Length
 - Weight-for-length (expressed as a percentile)
 - BMI
 - Weight-for-age z-score
 - Length-for-age z-score
 - Weight-for-length z-score
 - BMI-for-age z-score

Summary statistics for weight-for-age, length-for-age, and BMI-for-age percentiles may also be provided to aid interpretation of z-scores.

- LCI_{2.5} will be analyzed as a continuous variable using descriptive summary statistics and results (including changes from baseline) presented by visit. In the event that fewer than 3 subjects have these optional assessments available, listings of results may be provided instead of summary statistics.
- Markers of pancreatic inflammation (fecal elastase-1): These parameters will be summarized descriptively as a continuous parameter and results (including changes from baseline) presented by visit. Shifts from baseline will be summarized by visit.
- Marker of intestinal inflammation (fecal calprotectin). This parameter will be summarized descriptively as a continuous parameter and results (including changes from baseline) presented by visit.
- Qualitative microbiology cultures: the presence of bacteria will be descriptively summarized by subject counts and percentages by visit. Shifts from baseline may be presented, as appropriate.
- Pulmonary exacerbations: Pulmonary exacerbations (PE_x) will be identified using the definitions provided in Section 11.5.3 of the protocol, and will be analyzed in 3 ways, as follows:
 - The number of pulmonary exacerbations will be normalized to an annual period to adjust for differences in time spent on study and summarized as a continuous variable using descriptive summary statistics.
 - The number of days with pulmonary exacerbations (cumulative duration) will be normalized to an annual period to adjust for differences in time spent on study and summarized as a continuous variable using descriptive summary statistics.

- The time-to-first pulmonary exacerbation in 96 weeks, total treatment duration will be analyzed using the Kaplan-Meier method (provided the number of subjects with events observed is adequate) and the event-free rate.
- Rate of CF-related hospitalizations will be analyzed in 3 ways, as follows:

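### Pooled by-visit change-from-baseline rows mix intervals nominally 24 weeks apart, and SAP 2.1 does not log the changed rollover baseline

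*SAP*

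**What the plan says.** SAP 8.1 defines baseline in two ways. For one group, "the baseline value for rollover subjects (who participated in Study 124 Part B or Part A/B) is defined as the baseline measurement", and that measurement is the one taken in the parent study. For IVA-naive subjects, the group "who did not participate in Study 124 Part B or Part A/B) is defined as the most recent non-missing measurement collected", the cut-off is first study drug in Study 126. Table 11-4 in Appendix B repeats the parent-study baseline for every rollover assessment and makes no distinction between Same-day and Gap Transition.

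The groups are then combined. SAP 2.1 announces the pooling: "the final analysis will be based on the combined subjects from Study 124 Parts B and A/B, and subjects not from Study 124". SAP 8.3 says "all efficacy analyses described in this section will be based on the FAS, for the Ivacaftor Arm overall", and SAP 8.4 says "safety endpoints will be analyzed based on the Safety Set, for the total subjects in the Ivacaftor arm". Growth parameters are "summarized descriptively as continuous variables by visit (including change from baseline"), and for fecal elastase-1 "Shifts from baseline will be summarized by visit". Sweat chloride, laboratory, ECG and vital-sign changes are also reported by visit. Tables 11-4 and 11-5 share week labels and target days wherever both groups have a visit.

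The link between the studies is in SAP 6.1, Figure 6-1 footnote a, which states for Same-day subjects: "Week 24 Visit of Study 124 Part B or Part A/B will be the same day as the Day 1 Visit of Study 126". For Gap Transition, Day 1 comes later.

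Protocol 12.3.1 set different rules: change from both baselines for Same-day subjects, and from the Study 126 baseline only for Gap subjects. Protocol 12.3 presented results by source group, and 12.3.3.2 allowed either treatment duration or time on study as the time axis.

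**The concern.** A by-visit mean change is read as the change over the time named in its row. Here the row label gives time in Study 126, but for rollovers the change runs from the start of Study 124. A pooled mean then corresponds to no single interval since baseline.

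The subjects start treatment before 24 months of age, and protocol 9.2.3 notes that children gain weight as part of normal growth, so 24 extra weeks matter for raw weight, length and BMI. Laboratory values, vital signs and ECG intervals that change with age are exposed in the same way.

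The make-up of the rows also changes down a table. Growth Weeks 2, 4, 8 and 18 and sweat chloride Weeks 2 and 12 contain IVA-naive subjects only, and rollovers then join. A step between adjacent rows could reflect who is in the row. In a study with no inferential analysis these tables are the main result, so the risk is misreading.

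**Working it through.** **Inputs.** Baseline definitions: SAP 8.1. Windows and target days: SAP Tables 11-4 and 11-5. Offset between studies: SAP 6.1 footnote a. Visit tolerance of ±7 days: protocol Tables 3-1 to 3-3. Study day is taken to count from Study 126 Day 1 for both groups, which the Study 126 visit labels imply.

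**Step 1: the plan's target days.** 7 × week gives 84, 168, 252, 336, 420, 504, 588 and 672 for Weeks 12 to 96, matching both tables.

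**Step 2: nominal time since baseline.** Naive = W weeks; Same-day rollover = W + 24 weeks.

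| Study 126 week | Naive | Same-day rollover |
|---|---|---|
| 12 | 12 | 36 |
| 24 | 24 | 48 |
| 48 | 48 | 72 |
| 72 | 72 | 96 |
| 96 | 96 | 120 |

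With both Study 126 visits on schedule and 168 days in Study 124, the difference is 168 ± (7 + 7) = 154 to 182 days.

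**Step 3: can the analysis windows absorb it?** Add the offset to each Table 11-4 bound and compare with Table 11-5. The offset is 168 days if 24 full weeks are added. It is 167 if the Study 124 Week 24 Visit is study day 168, the SAP's own convention for Week 24, with first dose on day 1.

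| Row | Rollover + 168 | Naive | Offset 168 | Offset 167 |
|---|---|---|---|---|
| Growth, chemistry, hematology, vital signs: Week 12 | 170–294 | 71–105 | 65 days apart | 64 |
| Same: Week 24 | 295–378 | 148–210 | 85 apart | 84 |
| Same: Week 36 (Weeks 48–84 alike) | 379–462 | 211–294 | 85 apart | 84 |
| Sweat chloride: Week 24 | 170–420 | 127–252 | overlap 170–252 | overlap 169–252 |
| Sweat chloride: Week 48 | 421–588 | 253–420 | adjacent | touch at day 420 |
| Sweat chloride: Week 72 | 589–756 | 421–588 | adjacent | touch at day 588 |
| ECG: Week 24 | 170–420 | 127–210 | overlap 170–210 | overlap 169–210 |

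The growth-type windows never meet. If a subject's Study 124 period were only 161 days (an illustration), they would still be 163 − 105 = 58 days apart at Week 12. Sweat chloride Weeks 48 and 72 would then overlap by 7 days each.

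**Step 4: shift in the pooled row.** Mean elapsed time = W + 24p, where p is the rollover share of the row, all taken as Same-day. The documents do not give p. For assumed p = 0.25, 0.50 and 0.75 the shift is 6, 12 and 18 weeks.

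**Step 5: Gap rollovers at Week 24.** (168 + 168 + g)/7 weeks gives 48.1 for g = 1 day and 49.3 for g = 9 days (the laboratory-repeat cut in protocol 9.1.1.2.1). The documents state no cap on the gap. For these subjects elapsed time exceeds time on drug.

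**Step 6: which rows mix.** Growth, chemistry, hematology and vital signs mix from Week 12. Sweat chloride, fecal markers and microbiology mix from Week 24. ECG, as windowed, mixes at Weeks 24, 48, 72 and 96. By the protocol's schedule footnotes, multiple breath washout mixes at Weeks 24 and 48, and at Week 96 if the Week 96 footnotes apply.

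**Step 7: the log.** SAP 2.1 records the growth reference, ECG visits, Follow-up OE, dose determination, a z-score name and the pooling. It does not record that Gap rollovers move from the Study 126 to the Study 124 baseline, or that the Study 126 baseline is dropped for Same-day rollovers.

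**Step 8: rollover ECG windows (separate, minor).** SAP 2.1 says rollover ECGs at Weeks 12, 36, 60 and 84 will be presented. Table 11-4 has ECG windows only for Weeks 24, 48, 72 and 96. Target days 84 and 252 fall in the Week 24 window, 420 in Week 48 and 588 in Week 72. The by-visit summary keeps the record closest to target, so these ECGs are normally displaced.

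**The case against.** Much of this is an open and defensible choice. Measuring rollovers from before their Study 124 dosing is sensible, since a Study 126 baseline would follow 24 weeks of ivacaftor. SAP 8.1 states both definitions plainly, and the protocol permits time on study as the axis. These points stand, which is why the fix keeps the Study 124 baseline.

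A reader might infer that the SAP silently breaks protocol 12.3 on presentation by source group. It does not: SAP 2.1 logs the pooling, and that supersedes the by-source presentation. Only the two baseline departures are unlogged.

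The practical effect may also be modest. Z-scores adjust for age and sex. Protocol 5.3 describes the sweat chloride fall in Study 108 (ages 2 through 5) as quick and lasting, so 24 more weeks may matter little for the secondary endpoint. All subject data are listed and no test is planned. This limits the point mainly to raw growth and age-dependent safety measures, but a listing does not correct a summary mean that is misread.

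A reader might infer that the sweat chloride windows are fully separated after Week 24. That depends on the day convention: they are adjacent at an offset of 168 days and touch at 167. The growth-type separation survives either convention.

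On ECG, a reader might infer that the extra records are lost. They remain in the listings, and SAP 8.1 uses the worst record for threshold analyses. Only the by-visit summaries displace them.

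**Conclusion.** The point holds for by-visit change-from-baseline and shift tables in rows that contain both groups. Each mixes nominal intervals of W and W+24 weeks, with Gap rollovers longer still, and the two baseline departures from protocol 12.3.1 are unlogged. It should be fixed before database lock.

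It rests on a nominal 24 weeks between the Study 124 baseline and Study 126 Day 1, and on study day counting from Study 126 Day 1. One might read the rollover baseline as pre-ivacaftor for everyone, but the documents do not settle which baseline applies to Part A/B subjects, so their interval may differ from W+24.

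A reader might also infer a known bias in the reported means. The documents give no rollover share, number of Gap subjects or expected changes, so no effect in kg, mmol/L or msec can be derived. TEAE, cataract-incidence and annualised-rate summaries do not depend on this baseline and are unaffected. The ECG windows are a minor inconsistency between SAP 2.1 and Table 11-4.

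**What to change.** 1. Keep the Study 124 baseline and the overall column. Add separate rollover and IVA-naive columns to every by-visit change-from-baseline and shift table. Each column then has its own nominal interval, and a footnote can state that the rollover interval is W+24 weeks plus any gap.
2. In addition, log both baseline departures with reasons in SAP 2.1, or restore the protocol 12.3.1 change from the Study 126 baseline as a supplementary summary for rollovers. Logging alone leaves the mixed rows in place. The supplementary summary follows 24 weeks of Study 124 treatment, so it should not be pooled with the naive changes.
3. Separately, add Week 12, 36, 60 and 84 rollover ECG windows to Table 11-4 and narrow the neighbouring windows to suit. Those rows will then hold both groups, so the columns in item 1 apply to them too.

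The cost is SAP wording, extra columns in existing table shells and possibly a few more tables. No new data are needed. The drawback is a smaller n in each column.
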